5.3. Screening/Baseline Failures

Screen failures are defined as subjects who consent to participate in the clinical trial but are never subsequently randomized. In order to ensure transparent reporting of screen failure subjects, meet the Consolidated Standards of Reporting Trials (CONSORT) publishing requirements, and respond to queries from Regulatory authorities, a minimal set of screen failure information is required including Demography, Screen Failure details, Eligibility Criteria, and any Serious Adverse Events.

5.3.1. Re-Screening

If a subject has not met all of the Eligibility Criteria within the 28-day screening period, re-screening is allowed. Subjects are only allowed to be re-screened once; the entire screening process must be repeated (with the exception of chest X-ray if within 12 weeks of the first screening period or HRCT if this was already performed within the first screening period).

If a blood sample has to be withdrawn due to sample handling problems, breakage or sample integrity, this is not considered a re-screening.

Further details regarding the procedure for re-screening may be found in the SRM.

5.3.2. Re-Testing

5.3.2.1. Laboratory tests

If a subject fails any of the laboratory inclusion/exclusion criteria, the test may be repeated twice within the screening period. If the subject fails the laboratory criteria for a third time they will be considered a screen failure; these subjects may be re-screened as described in Section 5.3.1.

If a blood sample has to be withdrawn due to sample handling problems, breakage or sample integrity, this is not considered a re-testing.

Further details regarding the procedure for laboratory re-testing may be found in the SRM.

5.3.2.2. Pulmonary Function Tests

It is permitted to repeat the pulmonary function testing sessions (spirometry and/or D_{LCO}) once within the screening period. If the screening D_{LCO} result is $\geq 60\%$ but $< 70\%$ predicted, a chest HRCT must be performed. If this cannot be done within the screening window, then the subject must be re-screened.

5.3.2.3. ECG test

The ECG may be repeated once within the screening period if the recorded QTcF value was slightly out of range, and the Investigator does not consider that there are any other clinically-significant ECG abnormalities that would preclude the subject from participating in the study.

5.4. Withdrawal/Stopping Criteria

The following actions must be taken in relation to a subject who fails to attend the clinic for a required study visit:

- The site must attempt to contact the subject and re-schedule the missed visit as soon as possible.
- The site must counsel the subject on the importance of maintaining the assigned visit schedule and ascertain whether or not the subject wishes to and/or should continue in the study.
- In cases where the subject is deemed ‘lost to follow up’, the investigator or designee must make every effort to regain contact with the subject (where possible, 3 telephone calls and if necessary a certified letter to the subject’s last known mailing address). These contact attempts should be documented in the subject’s medical record.
- Should the subject continue to be unreachable, only then will he/she be considered to have withdrawn from the study with a primary reason of “Lost to Follow-up”.

A subject may withdraw from study treatment at any time at his/her own request, or may be withdrawn at any time at the discretion of the investigator for safety, behavioral or administrative reasons.

In addition, study medications will be discontinued and the subject withdrawn from the study in the event of any of the following:

- All serious or opportunistic infections.
- Pregnancy.
- Confirmed PAP.
- Severe or serious hypersensitivity reactions, including anaphylaxis.
- If the liver chemistry stopping criteria (Section 5.4.1) or QTc stopping criteria (Section 5.4.2) are met.
- Persistent or recurrent hematological laboratory abnormalities (see Section 5.5.2).
- Detected (≥ 2.1 log copies/mL) HBV DNA for subjects who have positive anti-HBs antibody.
- Other serious or severe adverse events, at the discretion of the investigator, after consultation with the Medical Monitor.

[figure not shown]
If a subject withdraws from the study, he/she may request destruction of any samples taken, and the investigator must document this in the site study records.

Any subject who withdraws must complete an early withdrawal visit, and the 10-week follow-up visit (from withdrawal visit).

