4.2. Treatment Arms and Duration

This study is composed of up to 4 weeks screening period, 12 weeks treatment period (last dose Week 10), and 10 weeks follow-up period (12 weeks from last dose).

Subjects will be randomized (1:1:1:1) to placebo or one of three subcutaneous (SC) GSK3196165 doses at Day 1 (Week 0).

Treatment with GSK3196165 or placebo will be given weekly as a single SC injection by an unblinded administrator. There will be 5 weekly injections (Day 1, 8, 15, 22, 29), then every other week (EOW) injections at Day 43, 57 and 71 (Week 6, 8, 10, respectively).

GSK3196165/placebo must be administered on the same day each week ± 1 day for the first 5 weekly doses. Following this GSK3196165 or placebo must be administered on the same day EOW ± 3 days.

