6.4. Blinding

The study will be double-blind, which means that the investigator and trial staff at site (apart from the unblinded administrator), subject, and sponsor personnel (apart from the unblinded monitor and the unblinded data manager) will be blinded to the trial treatment allocated to each individual subject.

There will be at least one unblinded administrator that will prepare and administer the study treatment and will not perform any other study procedures. A shield (e.g., eye mask) will be used during investigational product administration so that subjects are not able to see the injection volume, syringe size, or any difference in color between GSK3196165 and placebo.

Emergency Key Code Unblinding

- The investigator or treating physician may unblind a subject's treatment assignment **only in the case of an emergency** OR in the event of a serious medical condition when knowledge of the study treatment is essential for the appropriate clinical management or welfare of the subject as judged by the investigator.
- Investigators have direct access to the subject's individual study treatment.
- It is preferred (but not required) that the investigator first contacts the Medical Monitor or appropriate GSK study personnel to discuss options **before** unblinding the subject's treatment assignment.
- If GSK personnel are not contacted before the unblinding, the investigator must notify GSK as soon as possible after unblinding, but without revealing the treatment assignment of the unblinded subject, unless that information is important for the safety of subjects currently in the study.
- The date and reason for the unblinding must be fully documented in the eCRF.

A subject will be withdrawn if the subject's treatment code is unblinded by the investigator. The primary reason for discontinuation (the event or condition which led to the unblinding) will be recorded in the eCRF.

- GSK's Global Clinical Safety and Pharmacovigilance (GCSP) staff may unblind the treatment assignment for any subject with an SAE. If the SAE requires that an expedited regulatory report be sent to one or more regulatory agencies, a copy of the report, identifying the subject's treatment assignment, may be sent to investigators in accordance with local regulations and/or GSK policy.

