Lung biomarkers		X ⁴										X		X	X	
Immunogenicity (anti-GSK3196165 antibody) ¹⁷		X ⁴			X		X					X		X	X	
Anti-GM-CSF auto-antibodies		X ⁴														
Study Treatment GSK3196165/placebo ¹⁸		X		X	X	X	X	X	X	X						

ACPA: Anti-cyclic citrullinated protein antibody, CCP: Cyclic citrullinated peptide, ESR: Erythrocyte sedimentation rate, FVC: Forced vital capacity, HAQ-DI: Health Assessment Questionnaire Disability Index, HBV: Hepatitis B virus, HDL: High-density lipoprotein, LDL: Low-density lipoprotein, RF: Rheumatoid factor.

1. All subjects who withdraw from the study should have an early withdrawal (EW) visit as soon as possible after study agent discontinuation and then return for a follow-up visit (the last visit) for 10 weeks (12 weeks after last dose of study medication).
2. The same individual (where possible) should perform all disease assessments for an individual subject.
3. PRO assessments should be conducted before any tests, procedures, assessments or consultations, to avoid influencing the subjects' perception.
4. Assessments may be performed up to 24hours before dosing GSK3196165/placebo.
5. All safety evaluations should be conducted before dosing GSK3196165/placebo.
6. Height will be measured at only screening.
7. Complete physical at screening, and then limited physical examination (see Section [7.4.7](#)) thereafter.
8. ECG should be performed before vital signs, blood draws, and dosing (triplicate ECGs required at screening, and single thereafter unless there are safety concerns, in which case repeats may be required(see Section [7.4.9](#)).
9. Only SAEs related to study participation or related to a GSK product will be recorded from the time a subject consents to participate in the study.
10. Unless performed within previous 12 weeks (No need to repeat if subject re-screened).
11. Chest HRCT if $D_{LCO} \geq 60\% - <70\%$ predicted (No need to repeat if subject re-screened).
12. ≥ 8 hours fasting required before blood draw.
13. For women of child-bearing potential. S=serum; U=urine.
14. ESR measured locally.
15. PK sampling should be collected before dosing at the visits scheduled study treatment (GSK3196165/placebo). At the visits doesn't scheduled study treatments, it may be collected in any time during the visit. (Day 3, 74, 85, 106, 127, 155, and early withdrawal visit).
16. In consenting subjects.

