### 11.6.2.2. Handling of Missing Data for Statistical Analysis

Element	Reporting Detail
Continuous variables	
 
• The analysis will be considered on the assumption of Missing at Random (MAR) (e.g. MMRM).
 

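### Stopping study drug or emergency unblinding also ends study participation, which cuts post-dose AE, PK and HBV DNA contacts and usually the Week 12 DAS28(CRP), and the follow-up rules conflict with one another

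*Protocol*

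**What the plan says.** **Stopping and leaving are one step.** For a list that includes serious or opportunistic infection, severe hypersensitivity, liver and QTc criteria, persistent haematology abnormalities and detected HBV DNA, Protocol 5.4 states that "study medications will be discontinued and the subject withdrawn from the study in the event of any of the following". Section 5.4.2 withdraws subjects who meet a QTc criterion, and 6.4 adds: "A subject will be withdrawn if the subject's treatment code is unblinded by the investigator".

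**What is then scheduled.** Section 5.4 requires: "Any subject who withdraws must complete an early withdrawal visit, and the 10-week follow-up visit (from withdrawal visit". Footnote 1 of the Time and Events Table (7.1) says: "All subjects who withdraw from the study should have an early withdrawal (EW) visit as soon as possible after study agent discontinuation". It then has them "return for a follow-up visit (the last visit) for 10 weeks (12 weeks after last dose of study medication".

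**What completers have.** Section 4.2 gives "12 weeks treatment period (last dose Week 10), and 10 weeks follow-up period (12 weeks from last dose". PK samples at visits without dosing fall on "Day 3, 74, 85, 106, 127, 155, and early withdrawal visit". AEs are also collected at each of those visits. HBV DNA, in HBs Ab positive subjects, is scheduled at Visits 12 to 15 after the last dose.

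**How the data are used.** SAP Appendix 2 and 11.4.3 put out-of-window data in listings and keep them out of summaries and analyses. For continuous endpoints SAP 11.6.2.2 says: "The analysis will be considered on the assumption of Missing at Random (MAR) (e.g. MMRM". The dose-response models in SAP 8.2.2.1 use Week 12 change in DAS28(CRP) with dose as the only predictor. SAP Table 4 starts every AUC, and takes Cmax, from the Visit 10 (Day 71) dose.

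**The concern.** Scheduled ascertainment becomes thinner in the subjects who had a safety event. Their contacts after the last dose are fewer and further apart, and their Week 12 efficacy value is usually not obtained in window. The dose-response fit then omits them, with no earlier visit standing in. The MMRM keeps their earlier visits but has to assume MAR for values missing because of an adverse event. The SAP plans no sensitivity analysis for this.

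Section 5.4 also has no end date, and some of its criteria are tested after dosing is over. HBV DNA is scheduled four times after Day 71. As the schedule reads, the only routine on-study 12-lead ECG apart from the early withdrawal (EW) visit is at Week 12, 14 days after the last dose. A criterion met then can remove a subject from follow-up when no study drug is left to stop.

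**Working it through.** Nominal visit days are used throughout.

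**1. The plan's own follow-up figures.** Last dose Day 71, Week 12 = Day 85, last visit Day 155. (155 − 85)/7 = 10 weeks and (155 − 71)/7 = 12 weeks. Both match section 4.2.

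**2. Scheduled contacts after the last dose.**

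| | Completer | Withdrawn subject, minimum |
|---|---|---|
| Contacts (AE and PK) | Days 74, 85, 106, 127, 155 = 5 | EW and last visit = 2 |
| Longest gap | 155 − 127 = 28 days | 70 days by 5.4 |
| HBV DNA (HBs Ab positive) | Visits 12, 13, 14, 15 = 4 | EW and last visit = 2 |
| Full assessments | Visits 12 and 15 = 2 | EW and last visit = 2 |

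Visits attended between the last dose and the stop come on top of the two.

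**3. The two dates for the last visit.** Let EW be e days after the last dose. Section 5.4 puts the last visit at e + 70 days. Footnote 1, and the AE collection period in 7.4.3.1, put it at 84 days. They agree only if e = 14.
- e = 3: 73 days, 11 short of 84.
- e = 7: 77 days, 7 short of 84.

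The SAP counts AEs as on-treatment up to 12 weeks after the last dose for everyone (Appendix 3), so under 5.4 the last contact can come before that window closes.

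**4. Who still has a Week 12 value?** The window is Day 85 ± 3, i.e. Days 82 to 88.
- EW + 70 falls in it when EW is on Days 12 to 18.
- Last dose + 84 falls in it only for a last dose on Day 1 (1 + 84 = 85).
- EW itself falls in it when held on Days 82 to 88.

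Otherwise there is no in-window value. Each such subject is 1 of about 10, or 10% of an arm. The SAP does not say clearly whether an in-window EW or last visit counts as Week 12.

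**5. PK, stopped before Day 71.** The Visit 10 dose is not given, so Cmax, AUCtau, AUC(0-t) and AUC(0-inf) do not exist as the SAP defines them, whatever the follow-up. The cost to the power model uses SE(slope) = σ/√Σ n_k(ln D_k − mean)², with doses spaced by ln 2 = 0.693:
- 10, 10, 10 subjects: σ/√(20 × 0.4805) = 0.3226σ
- one lost at 180 mg: 0.3313σ, up 2.7%
- one lost per active arm: σ/√(18 × 0.4805) = 0.3400σ, up 5.4%

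Extra follow-up visits change none of these.

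**6. PK, criterion met after the Day 71 dose.** Take EW on Day 78 as an example. Samples after the dose are Day 74, Day 78 and the last visit: 3 instead of 5, with Days 85, 106 and 127 lost. AUCtau needs the 336-hour value (Day 85). It would be interpolated between Day 78 and Day 148 (5.4) or Day 155 (footnote 1). If the last sample is not quantifiable, it would be extrapolated from a slope resting on at most two post-dose points. If that slope cannot be estimated, SAP Table 4 leaves the remaining part uncalculated. AUC(0-inf) and t1/2 depend on the same slope.

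**7. Liver events.** Section 5.4 withdraws a subject who meets the liver stopping criteria. Protocol Appendix 3 stops study treatment but allows the subject to continue in the study for protocol-specified follow-up. Both cannot apply.

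**The case against.** The best case against the point is that two contacts is only a floor, in a study that tests no hypothesis. Section 7.4.3.3 follows SAEs and AESIs to resolution or stabilisation, 7.4.10 repeats clinically significant abnormal laboratory tests, and Appendix 3 adds weekly or twice-weekly liver monitoring. AE collection nominally runs to 12 weeks after the last dose for everyone, and full assessments are two in each group. DAS28(CRP) is secondary, and the sample size rests on feasibility. All of this stands. However, following an event does not schedule PK samples or a Week 12 DAS28(CRP), and it does not look for other events.

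Three stronger readings are tempting and are not supported:
- A reader might infer that subjects stopped early never have a Week 12 assessment. Step 4 shows that some do.
- A reader might infer that the rule thins the primary PK data in all early stoppers. Before Day 71 those parameters are lost because the dose is missing.
- A reader might infer that the AE window is cut short by design. Section 7.4.3.1 and the SAP keep it at 12 weeks; contacts are sparser, and only the timing wording of 5.4 can end them early.

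Applying 5.4 after the last dose is also partly inference, because its wording joins stopping drug to leaving the study. Sections 5.4.2 and 6.4 are not worded that way: they withdraw the subject outright.

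**Conclusion.** The point holds within these limits. Joining drug discontinuation, or unblinding, to study withdrawal lowers the scheduled minimum after the last dose from five contacts to two. The loss is in AE, PK and HBV DNA contacts. Most subjects stopped early drop out of the Week 12 dose-response fit, at about 10% of an arm each. Withdrawal itself harms the SAP's PK parameters only in subjects who meet a criterion after the Day 71 dose and before their remaining samples are taken. Separately, the documents contradict themselves on liver-stopped subjects and on when the last visit takes place.

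This rests on nominal visit days and on 5.4 being applied as written. The documents give no expected number of safety stops, so neither the size nor the direction of any bias can be stated. The change is worth making because it is cheap and the conflicting text has to be reconciled anyway.

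**What to change.** 1. In 5.4, 5.4.2, 6.4 and footnote 1, separate discontinuing study treatment from withdrawing from the study. Leave the stopping criteria unchanged.
2. Subjects who stop study drug and still consent keep the existing post-treatment AE, PK and HBV DNA contacts through 12 weeks after the last dose. They also have the Week 12 efficacy assessment on its original date.
3. State that a criterion met after the last dose does not end scheduled follow-up.
4. Reconcile 5.4 with Appendix 3 on liver events, and 5.4 with footnote 1 and 7.4.3.1 on the date of the last visit.
5. In the SAP, flag off-treatment DAS28 values, say before unblinding how the MMRM and dose-response fit use them, and say whether an in-window EW or last visit counts as Week 12.

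**Cost.** Wording, plus a few visits per early stopper. If the contacts follow the spacing of Visits 11 to 15 from the subject's own last dose, that is 5 − 2 = 3 more, plus a full Week 12 efficacy visit (joint counts, PROs, CRP, ESR) where none coincides. If subjects stay on the calendar schedule instead, there are 5 to 10 contacts within 12 weeks of the last dose (5 for a last dose on Day 57, 10 for Day 1). The change does not recover primary PK parameters in anyone stopped before Day 71.

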7.4.1. Study visits

Subjects will have systematic safety monitoring throughout the study. Additional time points for safety tests (such as vital signs, physical exams and laboratory safety tests) may be added during the course of the study based on newly available data to ensure appropriate safety monitoring.

In addition to routine laboratory assessments, ECG monitoring, and evaluation of adverse events, particular attention will be paid to respiratory events and function given the potential risk associated with targeting GM-CSF and the effects on alveolar macrophages. This may result in the occurrence of the extremely rare condition of PAP, which is characterized by the accumulation of surfactant lipids and protein in the alveolar spaces (with no fibrosis), with resultant impairment in gas exchange, which may lead to increase a risk of secondary pulmonary infections.

All subjects will return for a follow-up visit at 10 weeks after completion/withdrawal of treatment period. Particular attention will be paid to withdrawal symptoms given the potential risk associated with release of immune suppression.

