7.4.3.1. Time period and Frequency for collecting AE and SAE information

- AEs and SAEs will be collected from the start of Study Treatment until the follow-up contact (12 weeks after the last dose of investigational product), at the timepoints specified in the Time and Events Table (Section [7.1](#)).
- Medical occurrences that begin prior to the start of study treatment but after obtaining informed consent may be recorded on the Medical History/Current Medical Conditions section of the eCRF.
- Any SAEs assessed as related to study participation (e.g., protocol-mandated procedures, invasive tests, or change in existing therapy) or related to a GSK product will be recorded from the time a subject consents to participate in the study up to and including any follow-up contact.
- All SAEs will be recorded and reported to GSK within 24 hours, as indicated in [Appendix 5](#).
- Investigators are not obligated to actively seek AEs or SAEs in former study subjects. However, if the investigator learns of any SAE, including a death, at any time after a subject has been discharged from the study, and he/she considers the event reasonably related to the study treatment or study participation, the investigator must promptly notify GSK.

NOTE: The method of recording, evaluating and assessing causality of AEs and SAEs plus procedures for completing and transmitting SAE reports to GSK are provided in [Appendix 5](#).

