7.5. Immunogenicity

Serum samples will be collected and tested for presence of antibodies that bind to GSK3196165. Serum samples for testing anti-GSK3196165 antibodies will be collected as described in Section 7.1, Time and Events Table. The actual date and time of each blood sample collection will be recorded. Details of blood sample collection (including volume to be collected), processing, storage and shipping procedures are provided in the Study Reference Manual (SRM).

The timing and number of planned immunogenicity samples may be altered during the course of the study, based on newly-available data to ensure appropriate safety monitoring. In the event of a hypersensitivity reaction that is either 1) clinically-significant in the opinion of the investigator, or 2) leads to the subject withdrawing from the study, blood samples should be taken from the subject for immunogenicity testing, at the time of the event and again 12 weeks after. For subjects who prematurely withdraw from the study, immunogenicity testing will occur at withdrawal and at follow-up 12 weeks after last dose.

Serum will be tested for the presence of anti-GSK3196165 antibodies using the currently approved analytical methodology using a tiered testing schema: screening, confirmation and titration steps. The presence of treatment emergent anti-drug antibodies (ADA) will be determined using a GSK3196165 bridging style ADA assay with a bio-analytically determined cut point determined during assay validation. Samples taken after dosing with GSK3196165 that have a value at or above the cut-point will be considered treatment-emergent ADA-positive. These ADA positive samples will be further evaluated in a confirmatory assay, and confirmed positive samples will be further characterized by assessment of titer. Results of anti-GSK3196165 antibody testing will be reported at the end of the study and will include incidence and titer. The presence or absence of antibodies to GSK3196165 in dosed subjects will be analyzed, then summarized descriptively and/or graphically presented.

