#### Flowchart

### 11.3.1.2. Treatment States for AE Data

Treatment State	Definition
Pre-Treatment	AE Start Date < Study Treatment Start Date
On-treatment	Study Treatment Start Date ≤ AE Start Date ≤ Study Treatment Stop Date + 12 weeks
Post-treatment	AE Start Date > Study Treatment Stop Date + 12 weeks
Onset Time Since 1 st Dose (Days)	If Treatment Start Date > AE Onset Date, = AE Onset Date - Treatment Start Date If Treatment Start Date ≤ AE Onset Date, = AE Onset Date - Treatment Start Date + 1 Missing otherwise.
Onset Time Since last Dose (Days)	If Treatment Stop Date > AE Onset Date, = AE Onset Date - Treatment Stop Date If Treatment Stop Date ≤ AE Onset Date, = AE Onset Date - Treatment Stop Date + 1 Missing otherwise
Duration (Days)	AE Resolution Date – AE Onset Date + 1
Drug-related	If relationship to GSK3196165/Placebo is marked 'YES' on Inform/CRF OR value is missing.
MTX-related	If relationship to Methotrexate is marked 'YES' on Inform/CRF OR value is missing.

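### The last visit of subjects who withdraw early has two anchors, 10 weeks from the withdrawal visit and 12 weeks after the last dose, which agree only if withdrawal is seen exactly 14 days after that dose

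*Protocol*

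**What the plan says.** For subjects who complete treatment, Protocol Section 4.2 describes "12 weeks treatment period (last dose Week 10), and 10 weeks follow-up period (12 weeks from last dose". The 10-week and 12-week figures are two descriptions of one visit.

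For subjects who withdraw, the documents use two anchors:

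- **From withdrawal.** Section 5.4 requires an early withdrawal visit "and the 10-week follow-up visit (from withdrawal visit". Section 7.4.1 says the same for everyone: "All subjects will return for a follow-up visit at 10 weeks after completion/withdrawal of treatment period".
- **From the last dose.** Section 7.4.3.1 collects AEs and SAEs "until the follow-up contact (12 weeks after the last dose of investigational product". Section 7.5 states, for premature withdrawals, that "immunogenicity testing will occur at withdrawal and at follow-up 12 weeks after last dose". SAP Section 11.3.1.2 counts an AE as on-treatment up to "Study Treatment Stop Date + 12 weeks".
- **Both at once.** Footnote 1 of the Time and Events Table (Section 7.1, repeated in SAP Section 11.1.1) tells withdrawn subjects to "return for a follow-up visit (the last visit) for 10 weeks (12 weeks after last dose of study medication".

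The same footnote places the "early withdrawal (EW) visit as soon as possible after study agent discontinuation". It gives no number of days from the last dose to that visit.

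**The concern.** The completers' equality between 10 and 12 weeks has been carried over to withdrawn subjects, where nothing makes it true. A site that follows Section 5.4 to the letter can close out a subject before the period named in Sections 7.4.3.1 and 7.5 and in the SAP has ended. After that visit the Time and Events Table schedules no further contact, and Section 7.4.3.1 does not oblige investigators to look for events in former subjects. New events in the remaining days would then depend largely on spontaneous reports.

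The incidence of AEs, SAEs and AEs of special interest is a primary endpoint (Protocol Section 3), and the SAP's AE summaries are restricted to the on-treatment window (SAP Section 7.2). Section 5.4 makes serious or opportunistic infection, severe or serious hypersensitivity, and liver, QTc and haematological criteria grounds for withdrawal, so the affected subjects include those with the events of most interest. With 10 subjects per group, one subject is 10 percentage points of an incidence figure. A site following Section 5.4 could also miss the ADA time point in Section 7.5.

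**Working it through.** **Inputs.** Last dose Day 71, Week 12 visit Day 85, last visit Day 155 (Protocol Section 7.1). Doses on Days 1, 8, 15, 22, 29, 43, 57 and 71 (Section 4.2). Withdrawn subjects: last visit 10 weeks = 70 days after the withdrawal visit (Section 5.4). Observation window: 12 weeks = 84 days after the last dose (Sections 7.4.3.1 and 7.5; SAP Section 11.3.1.2, reading the treatment stop date as the date of the last dose).

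**Step 1: the plan's own figure, for completers.**
- Day 155 − Day 85 = 70 days = 10 weeks after the Week 12 visit.
- Day 155 − Day 71 = 84 days = 12 weeks after the last dose.

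The stated equality is reproduced. It holds because Day 85 − Day 71 = 14 days.

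**Step 2: withdrawn subjects under Section 5.4.** Let L be the days from the last dose to the withdrawal visit.
- Last visit, in days after the last dose = L + 70.
- Difference from the window = (L + 70) − 84 = L − 14.

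| L (days) | Last visit (days after last dose) | Difference from 84 days |
|---|---|---|
| 0 | 70 | 14 short |
| 3 | 73 | 11 short |
| 7 | 77 | 7 short |
| 10 | 80 | 4 short |
| 14 | 84 | none |
| 21 | 91 | 7 beyond |
| 28 | 98 | 14 beyond |

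As a share of the window, 14/84 = 17% and 4/84 = 5%.

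**Step 3: footnote 1 read literally.** A last visit 84 days after the last dose is 84 − L days after the withdrawal visit: 84 days at L = 0, 77 at L = 7 and 70 at L = 14. Only the last is 10 weeks, so the footnote's two figures conflict for every other L.

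**Step 4: an illustration, assuming the withdrawal visit takes place at the next planned dosing or Week 12 visit.**
- After the doses on Days 1, 8, 15 and 22, the next visit is 7 days later: last visit at 77 days, 7 short.
- After the doses on Days 29, 43, 57 and 71, it is 14 days later: last visit at 84 days, no gap.

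**Step 5: visit allowance.** The allowance row of the table is broken in the text available. If its ±1 week applies to the last visit, L = 0 gives 63 to 77 days, which never reaches 84; completers range from 77 to 91 days.

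**The case against.** The strongest reply is that the 12-week point is already specified. Protocol Section 7 says exact timings are in the Time and Events Table, footnote 1 there mentions 12 weeks after the last dose for this very visit, and Section 7.5 sets the withdrawn subjects' ADA follow-up at that time. It is therefore wrong to say that the plan simply sets the visit short. That stands. But the footnote also says 10 weeks, Sections 5.4 and 7.4.1 say only 10 weeks, and a site cannot tell from the text which governs.

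A reader might infer three stronger things, none of which the documents support:

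- *That withdrawal visits will usually fall within 14 days of the last dose.* No distribution of L is given. After half of the eight doses the next planned visit is 14 days later, and a dose suspension under Section 5.5 could make L longer than 14, giving a visit after the window.
- *That ADA and PK results are compromised by early samples with more residual drug.* If Section 7.5 is followed, the ADA sample is on time. The documents give no human half-life or assay drug tolerance from which to size an effect. The SAP derives its PK parameters from the Visit 10 dose onward (SAP Table 4), so subjects withdrawn before then contribute none.
- *That AE rates have a wrong denominator.* The planned summaries are numbers and percentages of subjects, not person-time rates, and the SAP classifies events by start date. SAEs and AEs of special interest already reported are followed to resolution or stabilisation (Section 7.4.3.3). What can be lost is a new event starting between the last visit and day 84.

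If the ±1 week allowance applies, a completer can also be seen at 77 days. That narrows the contrast with completers but does not remove the contradiction.

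**Conclusion.** The point holds as an internal contradiction. One visit has two anchors that agree only at L = 14 days, and the footnote that equates them fixes no such interval. The size is a possible shortfall of 14 − L days when L is below 14, so at most 14 of 84 days before any visit allowance. It is zero at 14 days and becomes an overshoot beyond that.

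This rests on two assumptions: that a site follows Section 5.4 rather than Section 7.5 or the 12-week part of footnote 1, and that the SAP's treatment stop date is the last dose date. How many of the 40 subjects would be affected cannot be derived from the documents. The consequence is modest, but it touches the observation period of a primary safety endpoint in small groups, so it is worth correcting.

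**What to change.** Reconcile Protocol Sections 5.4, 7.4.1, 7.4.3.1 and 7.5, footnote 1 of the Time and Events Table (and its copy in SAP Section 11.1.1), and the on-treatment definition in SAP Section 11.3.1.2. The final visit of withdrawn subjects and the end of AE and ADA observation should be defined from one stated anchor. Footnote 1 should no longer present 10 and 12 weeks as interchangeable for these subjects unless the interval from last dose to withdrawal visit is also fixed. Which anchor to use is for the sponsor to decide.

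The cost is a wording change in the protocol and, depending on the anchor chosen, in the SAP. The visit already exists, so no new assessment is needed.
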